**5.5.4****Selection and Timing of Dose for Each Subject**

Subjects will be randomly assigned to one of the six treatment groups (ABT-494 3 mg BID, ABT-494 6 mg BID, ABT-494 12 mg BID, ABT-494 24 mg BID, ABT-494 24 mg QD, placebo) at Baseline by the IRT system as described in Section [5.5.3](#).

Subjects should take study medication as outlined in Section [5.5.1](#).

Each subject's dosing schedule should be closely monitored by the site at each study visit by careful review of the subject's dosing diary. This will ensure that all subjects enrolled into the study maintain their original dosing schedule beginning with the first dose of study drug (Baseline/Week 0).

If a subject should forget to take their study drug dose at their regularly scheduled dosing time, they should take the forgotten dose as soon as they remember the dose was missed as long as it is at least 6 hours before their next scheduled dose. If a subject only remembers the missed dose within 6 hours before next scheduled dose, the subject should skip the missed dose and take the next dose at the scheduled time. If the subject experiences a study drug interruption > 10 days, they should notify their study site physician, and the Investigator should consult with the study designated physician about discontinuing the subject from the study.

**5.5.5****Blinding**

The Investigator, study site personnel, the subject and all AbbVie personnel with direct oversight of the conduct and management of the trial (with the exception of AbbVie Drug Supply Management Team) will remain blinded to each subject's treatment throughout the course of the study. The IRT will provide access to blinded subject treatment information in the case of a medical emergency. In the event of medical situation that requires unblinding of the study drug assignment the Investigator is requested to contact the AbbVie Study Designated Physician (SDP) prior to breaking the blind, as long as this communication does not compromise subject safety. However, if an urgent therapeutic intervention is necessary which warrants breaking the blind prior to contacting AbbVie

SDP, the Investigator can directly access the IRT system to break the blind without AbbVie agreement. In the event that the blind is broken before notification to AbbVie SDP, it is requested that the AbbVie SDP be notified within 24 hours of the blind being broken. Also, the date and reason that the blind was broken must be recorded in the source documentation and eCRF, as applicable. Throughout the duration of the double-blind periods of the study, the Investigator, site personnel, and subjects will remain blinded to the subject's treatment group. AbbVie will remain blinded to the induction and extension periods data until those data are locked and analyzed as part of the first and potentially second interim analysis, respectively.

#### **5.5.5.1                   Blinding of Investigational Product**

In order to maintain the blind, the ABT-494 capsules and Placebo capsules provided for the study will be identical in appearance.

#### **5.5.5.2                   Blinding of Data for Independent Data Monitoring Committee (IDMC)**

Data will be unblinded for review by the Independent Data Monitoring Committee (IDMC) by an unblinded statistician not involved in the planning, execution or analysis of the study. The process for unblinding study data and ensuring its confidentiality will be described in the Independent Data Monitoring Committee Charter for this study. The IDMC will advise the sponsor as to study continuation and/or modification.

#### **5.5.6                   Treatment Compliance**

The investigator or his/her designated and qualified representatives will administer/dispense study drug only to subjects enrolled in the study in accordance with the protocol. The study drug must not be used for reasons other than that described in the protocol.

Subject dosing will be recorded on a subject dosing diary. Subjects will be instructed to return all drug containers (even if empty) to the study site personnel at each clinic visit. The study site personnel will document compliance in the study source documents.

---

**5.5.7                   Drug Accountability**

In addition, an IRT will be used to document investigational product accountability including but not limited to date received, the lot number, kit number(s), date dispensed, subject number and the identification of person dispensing the drug.

All empty study drug blister cards will be inventoried by the site and verified by the site monitor. Empty study drug blister cards should be returned by the subject at each visit for accountability and compliance purposes and new containers issued as necessary. Empty blister cards will be retained until the site monitor is on site to confirm the returned medication. Site monitor(s) and site staff will complete study medication accountability via IRT source documents, subject dosing diaries, and by visually inspecting the blister cards whenever possible. After drug accountability has been completed, unused medication will be destroyed on site according to local procedures or regulations or returned to the destruction depot by the site monitor. A copy of the destruction methodology should be maintained at the site's facility.

**5.6                   Discussion and Justification of Study Design**

ABT-494 is a potent JAK1 selective inhibition that has been associated with endoscopic improvement and healing of the intestinal mucosa in preclinical animal models. More recently, filgotinib, a JAK1 inhibitor in Phase 2 clinical development in Crohn's disease was associated with superior clinical remission versus placebo. This study included subjects who could have been inadequate responders or intolerant to either immunomodulators or anti-TNF therapies. Of note, this treatment effect was more prominent in subjects who have inadequate responders to immunomodulators only. AbbVie proposes to include this patient population to assess the effect of ABT-494 and whether they would benefit the most from such therapy.

The proposed study is a 52-week, randomized, double-blind, placebo-controlled study to compare multiple doses of ABT-494 versus placebo in moderately to severely active CD patients with failure or intolerance to immunomodulators or anti-TNF biologic therapy. In order to assess the potential of ABT-494 to benefit patients with CD, we will enroll

patients with active disease (confirmed by central reading of endoscopy video) and assess the potential of ABT-494 to induce clinical remission and endoscopic improvement. The 16-week induction therapy period is generally accepted as the timeframe during which an effective treatment would be expected to produce clinical benefit in CD.

During the double-blind extension phase of this study, all patients will have an opportunity to be treated with ABT-494 in order to assess the potential of ABT-494 to maintain clinical remission in patients who have responded to treatment with ABT-494.

### **5.6.1      Appropriateness of Measurements**

Standard statistical, clinical, and laboratory procedures will be utilized in this study. All efficacy measurements in this study are standard for assessing disease activity in subjects with CD. All clinical and laboratory procedures in this study are standard and generally accepted. Central reading of endoscopy films will increase study rigor and ensure enrollment of patients with active inflammation.

### **5.6.2      Suitability of Subject Population**

Adult male and female subjects with active CD who meet all inclusion criteria and none of the exclusion criteria are eligible for this study. The specific subject population chosen was based on the unmet medical need for subjects with evidence of mucosal inflammation and who have had an inadequate response or intolerance to immunomodulators or anti-TNF biologic therapy.

### **5.6.3      Selection of Doses in the Study**

This study is designed to evaluate the efficacy and safety/tolerability of ABT-494 in subjects with CD and to define the dose response profile of this compound. The dose selection for ABT-494 in the present study was based on the preliminary analysis of PK, PD, safety and tolerability data from the single ascending dose study of ABT-494 in healthy subjects (single doses ranging from 1 to 48 mg), the multiple ascending dose study of ABT-494 in healthy subjects (multiple doses ranging from 3 to 24 mg BID for 14 days), as well as the multiple dose study of tofacitinib 5 mg BID for 14 days in healthy

subjects. Based on ex-vivo experiments conducted during the Phase 1 studies, we know that doses selected for this study significantly inhibit IL-6 signaling via the JAK1 pathway. In addition, the dose range selected has been shown to be well tolerated in healthy volunteers and includes exposure anticipated to result in JAK1 selective exposure that may produce both efficacy and favorable benefit:risk profile. Study drug will be dosed for 52 weeks and will not exceed 24 mg BID.

During the extension Phase, the ability of ABT-494 to maintain patients in remission will be assessed, with opportunity for dose escalation to the highest induction dose planned, if needed for a specific patient.

## **6.0 Complaints**

A Complaint is any written, electronic, or oral communication that alleges deficiencies related to the physical characteristics, identity, quality, purity, potency, durability, reliability, safety, effectiveness, or performance of a product/device after it is released for distribution.

Complaints associated with any component of this investigational product must be reported to the Sponsor (Section [6.2.2](#)). For adverse events, please refer to Sections [6.1](#) through [6.1.7](#). For product complaints, please refer to Section [6.2](#).

### **6.1 Medical Complaints**

The investigator will monitor each subject for clinical and laboratory evidence of adverse events on a routine basis throughout the study. The investigator will assess and record any adverse event in detail including the date of onset, event diagnosis (if known) or sign/symptom, severity, time course (end date, ongoing, intermittent), relationship of the adverse event to study drug, and any action(s) taken. For serious adverse events considered as having "no reasonable possibility" of being associated with study drug, the investigator will provide an Other cause of the event. For adverse events to be considered intermittent, the events must be of similar nature and severity. Adverse events, whether in

response to a query, observed by site personnel, or reported spontaneously by the subject will be recorded.

All adverse events will be followed to a satisfactory conclusion.

### **6.1.1      Definitions**

#### **6.1.1.1      Adverse Event**

An adverse event (AE) is defined as any untoward medical occurrence in a patient or clinical investigation subject administered a pharmaceutical product and which does not necessarily have a causal relationship with this treatment. An adverse event can therefore be any unfavorable and unintended sign (including an abnormal laboratory finding), symptom, or disease temporally associated with the use of a medicinal (investigational) product, whether or not the event is considered causally related to the use of the product.

Such an event can result from use of the drug as stipulated in the protocol or labeling, as well as from accidental or intentional overdose, drug abuse, or drug withdrawal. Any worsening of a pre-existing condition or illness is considered an adverse event.

Worsening in severity of a reported adverse event should be reported as a new adverse event. Laboratory abnormalities and changes in vital signs are considered to be adverse events only if they result in discontinuation from the study, necessitate therapeutic medical intervention, (meets protocol specific criteria [see Section [6.1.7](#) regarding toxicity management]) and/or if the investigator considers them to be adverse events.

An elective surgery/procedure scheduled to occur during a study will not be considered an adverse event if the surgery/procedure is being performed for a pre-existing condition and the surgery/procedure has been pre-planned prior to study entry. However, if the pre-existing condition deteriorates unexpectedly during the study (e.g., surgery performed earlier than planned), then the deterioration of the condition for which the elective surgery/procedure is being done will be considered an adverse event.

### 6.1.1.2      **Serious Adverse Events**

If an adverse event meets any of the following criteria, it is to be reported to AbbVie as a serious adverse event (SAE) within 24 hours of the site being made aware of the serious adverse event.

Death of Subject	An event that results in the death of a subject.
Life-Threatening	An event that, in the opinion of the investigator, would have resulted in immediate fatality if medical intervention had not been taken. This does not include an event that would have been fatal if it had occurred in a more severe form.
Hospitalization or Prolongation of Hospitalization	An event that results in an admission to the hospital for any length of time or prolongs the subject's hospital stay. This does not include an emergency room visit or admission to an outpatient facility.
Congenital Anomaly	An anomaly detected at or after birth, or any anomaly that results in fetal loss.
Persistent or Significant Disability/Incapacity	An event that results in a condition that substantially interferes with the activities of daily living of a study subject. Disability is not intended to include experiences of relatively minor medical significance such as headache, nausea, vomiting, diarrhea, influenza, and accidental trauma (e.g., sprained ankle).

Important Medical Event Requiring Medical or Surgical Intervention to Prevent Serious Outcome	An important medical event that may not be immediately life-threatening or result in death or hospitalization, but based on medical judgment may jeopardize the subject and may require medical or surgical intervention to prevent any of the outcomes listed above (i.e., death of subject, life-threatening, hospitalization, prolongation of hospitalization, congenital anomaly, or persistent or significant disability/incapacity). Additionally, any elective or spontaneous abortion or stillbirth is considered an important medical event. Examples of such events include allergic bronchospasm requiring intensive treatment in an emergency room or at home, blood dyscrasias or convulsions that do not result in inpatient hospitalization, or the development of drug dependency or drug abuse.
--	--

For serious adverse events with the outcome of death, the date and cause of death will be recorded on the appropriate case report form.

### **6.1.2 Adverse Event Severity**

The investigator will use the following definitions to rate the severity of each adverse event:

Mild	The adverse event is transient and easily tolerated by the subject.
Moderate	The adverse event causes the subject discomfort and interrupts the subject's usual activities.
Severe	The adverse event causes considerable interference with the subject's usual activities and may be incapacitating or life-threatening.

### **6.1.3 Relationship to Study Drug**

The investigator will use the following definitions to assess the relationship of the adverse event to the use of study drug:

Reasonable Possibility	After consideration of factors including timing of the event, biologic plausibility, clinical judgment, and potential alternative causes, there is sufficient evidence (information) to suggest a causal relationship.
No Reasonable Possibility	After consideration of factors including timing of the event, biologic plausibility, clinical judgment, and potential alternative causes, there is insufficient evidence (information) to suggest a causal relationship.

[figure not shown]
For causality assessments, events assessed as having a reasonable possibility of being related to the study drug will be considered "associated." Events assessed as having no reasonable possibility of being related to study drug will be considered "not associated." In addition, when the investigator has not reported a causality or deemed it not assessable, AbbVie will consider the event associated.

If an investigator's opinion of no reasonable possibility of being related to study drug is given, an Other cause of event must be provided by the investigator for the serious adverse event.

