### **8.1.7.1 General Considerations**

Safety analyses will be carried out using the safety analysis set, which includes all subjects who receive at least one dose of study medication. Incidence of adverse events, including those related to study drug, changes in vital signs, physical examination results, ECGs, and clinical laboratory values will be analyzed.

Treatment-emergent adverse events will be tabulated by system organ class (SOC) and by the Medical Dictionary for Regulatory Activities (MedDRA) preferred term for each treatment group. Mean change from Baseline for laboratory and vital signs data will be summarized.

Missing safety data will not be imputed.

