### **8.1.7.2 Analysis of Adverse Events**

#### **8.1.7.2.1 Treatment-Emergent Adverse Events**

Adverse events (AEs) will be coded using the Medical Dictionary for Regulatory Activities (MedDRA) dictionary. Treatment-emergent adverse events, defined as AEs that began or worsened in severity after initiation of study drug in each period of the study, will be tabulated by system organ class (SOC) and MedDRA preferred term for each treatment group.

Adverse events starting more than 30 days following discontinuation of study drug will not be included in summaries of treatment-emergent AEs. When summarizing adverse events by relationship or severity, if a subject has an event with unknown severity or relationship then the subject will be counted in the severity/relationship category of "unknown" even if the subject has a second occurrence of the same event with a severity/relationship present. The only exception is if the subject has a second occurrence of the same event with the most extreme severity (i.e., "severe") or a relationship categories of "reasonable possibility." In this case, the subject will be counted under these most extreme severity/relationship categories.

Subjects reporting more than one AE for a given MedDRA preferred term will be counted only once for that term using the most severe incident in each study period. Subjects reporting more than one type of event within an SOC will be counted only once for that SOC.

Frequencies and percentages of subjects with treatment-emergent AEs will be summarized for each treatment group as follows:

- Any event
- By system organ class, and preferred term
- By system organ class, preferred term and maximum relationship
- By system organ class, preferred term and maximum severity
- Any event and by system organ class and preferred term for events resulting in death
- Any event and by system organ class and preferred term for events resulting in study drug discontinuation
- Any event and by system organ class and preferred term for serious events
- Any event and by system organ class and preferred term for adverse events with a relationship of "reasonable possibility"
- Any event and by system organ class and preferred term for adverse events of special interest (infection, opportunistic infection, and gastrointestinal perforations, malignancies and drug related hepatic disorders)

All AEs leading to early termination of study drug will be presented in listing format.

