11.2 Analysis of Adverse Events**11.2.1 Treatment-Emergent Adverse Events**

Treatment-emergent AE for double-blind Extension Phase is defined as any adverse event with an onset date on or after the first dose of double-blind maintenance dose and prior to the open-label dose or up to 30 days after the last dose of double-blind maintenance dose if subject discontinued prematurely in double-blind maintenance phase.

For subjects who entered open-label due to inadequate response, treatment-emergent AEs for open-label Extension Phase will also be summarized by open-label dose. Treatment-emergent AE for open-label Extension Phase is defined as any adverse event with an onset date on or after the first dose of open-label dose and up to 30 days after the last dose of open-label dose.

An overview of treatment-emergent AEs, including AEs of special interest such as adverse events leading to death and adverse events leading to early termination, AEs by

Medical Dictionary for Drug Regulatory Activities (MedDRA version 20.0 or later) preferred term and system organ class, AEs by maximum relationship to study drug, and AEs by maximum severity will be summarized by number and percentage.

Changes in laboratory data will be summarized.

In addition, shift tables and listings will be provided for abnormal values, whereby the normal range of the analyzing laboratory will be used. Vital signs will be analyzed similarly.

The number and percent of subjects experiencing treatment-emergent adverse events will be summarized for the following adverse event categories.

- Any treatment-emergent adverse event.
- Any treatment-emergent adverse event that was rated as possibly related to study drug by the investigator (Reasonable Possibility).
- Any treatment-emergent severe adverse event.
- Any treatment-emergent serious adverse event.
- Any treatment-emergent adverse event leading to discontinuation of study drug.
- Any treatment-emergent adverse event leading to death.
- Any treatment-emergent adverse event of special interest.

Treatment-emergent adverse events will be summarized as follows:

- Grouped by System Organ Class and Preferred Term.
- Grouped by System Organ Class, Preferred Term and Severity.
- Grouped by System Organ Class, Preferred Term and Relationship to Study Drug.
- Grouped by System Organ Class and Preferred Term with subject numbers.

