In treatment-emergent AE tables, a subject who reports more than one treatment-emergent AE in different system organ classes will be counted only once in the overall total. A subject who reports two or more different preferred terms which are in the same SOC will be counted only once in the SOC total. A subject who reports more than one treatment AE with the same preferred term will be counted only once for that preferred term using the most extreme incident (i.e., most "severe" for the severity tables and most "related" for the relationship tables).

Adverse events will also be summarized by maximum severity. If a subject has an adverse event with unknown severity, then the subject will be counted in the severity category of "unknown," even if the subject has another occurrence of the same adverse event with a severity present. The only exception is if the subject has another occurrence of the same adverse event with the most extreme severity – "Severe." In this case, the subject will be counted under the "Severe" category.

Adverse events will also be summarized by maximum relationship to study, as assessed by the investigator. If a subject has an adverse event with unknown relationship, then the subject will be counted in the relationship category of "unknown," even if the subject has another occurrence of the same adverse event with a relationship present. The only exception is if the subject has another occurrence of the same adverse event with a relationship assessment of "Reasonable Possibility." In this case, the subject will be counted under the "Reasonable Possibility" category, respectively.

Incidence rates per 100 patient years of exposure to study drug will be presented for AE overviews and for AEs by SOC and preferred term where the number of events will be used as the numerator.

$$100 \times \frac{\text{Number of TEAEs}}{\text{Total Patient Years}}$$

where total patient years is defined as the sum of the study drug exposure of all subjects, as defined in an earlier section, normalized by 365.25, and rounded to 1 decimal place.

Overview of treatment-emergent adverse events and treatment-emergent adverse events during the administration of ABT-494 grouped by System Organ Class and Preferred Term will also be summarized for the Any ABT-494 analysis set by quartile of average daily dose.

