Treatment-emergent adverse events will be summarized as follows:

- Grouped by System Organ Class and Preferred Term.
- A by-subject listing will be provided.
- Grouped by System Organ Class, Preferred Term and Severity.
- Grouped by System Organ Class, Preferred Term and Relationship to Study Drug.
- Grouped by System Organ Class and Preferred Term with subject numbers.

In treatment-emergent AE tables, a subject who reports more than one treatment-emergent AE in different system organ classes will be counted only once in the overall total. A subject who reports two or more different preferred terms which are in the same SOC will be counted only once in the SOC total. A subject who reports more than one treatment AE with the same preferred term will be counted only once for that preferred term using the most extreme incident (i.e., most "severe" for the severity tables and most "related" for the relationship tables).

Adverse events will also be summarized by maximum severity. If a subject has an adverse event with unknown severity, then the subject will be counted in the severity

category of "unknown," even if the subject has another occurrence of the same adverse event with a severity present. The only exception is if the subject has another occurrence of the same adverse event with the most extreme severity – "Severe." In this case, the subject will be counted under the "Severe" category.

Adverse events will also be summarized by maximum relationship to study, as assessed by the investigator. If a subject has an adverse event with unknown relationship, then the subject will be counted in the relationship category of "unknown," even if the subject has another occurrence of the same adverse event with a relationship present. The only exception is if the subject has another occurrence of the same adverse event with a relationship assessment of "Reasonable Possibility." In this case, the subject will be counted under the "Reasonable Possibility" category, respectively.

Incidence rates per 100 patient years of exposure to study drug will be presented for AE overviews and for AEs by SOC and preferred term where the number of events will be used as the numerator.

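### Protocol 6.1.3 treats an adverse event without a causality rating as associated with study drug, but the analysis rules count it as unknown and leave it out of the drug-related summaries

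*Protocol*

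**What the plan says.** Protocol 6.1.3 gives the investigator two causality categories and maps them to associated and not associated. It then covers the remaining case: "when the investigator has not reported a causality or deemed it not assessable, AbbVie will consider the event associated". The sentence is not restricted to serious events or to expedited reporting.

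Protocol 8.1.7.2.1, on the summaries by relationship or severity, says that "if a subject has an event with unknown severity or relationship then the subject will be counted in the severity/relationship category of" *unknown*. One exception follows: a second occurrence of the same event rated Reasonable Possibility moves the subject to that category. The same section plans a drug-related table by system organ class (SOC) and preferred term, restricted to events rated Reasonable Possibility.

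Section 11.2.1 of each SAP repeats the rule and its exception: "If a subject has an adverse event with unknown relationship, then the subject will be counted in the relationship category of" *unknown*. The drug-related overview row in each SAP is defined as "Any treatment-emergent adverse event that was rated as possibly related to study drug by the investigator (Reasonable Possibility").

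Protocol 8.1.7.1 adds a general statement: "Missing safety data will not be imputed".

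**The concern.** An event for which the investigator gave no causality is associated under one section of the protocol and unknown under another. Under the second rule it does not enter the drug-related table or the overview row, which are where a reader looks for events attributed to the drug.

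The 6.1.3 rule is the cautious one, since doubt counts towards the drug. The tabulation rule can only give the same drug-related count or a lower one. In the induction period the overview row is also compared with placebo by Fisher's exact test, with P values below 0.100 shown, so the classification feeds a reported comparison.

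**Working it through.** The documents state no figure to reproduce. The check is a comparison of texts, followed by a small illustration.

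**1. Same event, two rules.** Take an event with no causality reported.

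| Place | Treatment of the event |
|---|---|
| Protocol 6.1.3 | Associated |
| Protocol 8.1.7.2.1, by-relationship summary | Unknown, unless the same event also occurs with Reasonable Possibility |
| Protocol 8.1.7.2.1, drug-related table | Not included |
| Induction SAP 11.2.1, by-relationship table | Unknown, same exception |
| Induction SAP 11.2.1, overview row | Not included |
| Extension SAP 11.2.1, by-relationship table | Unknown, same exception |
| Extension SAP 11.2.1, overview row | Not included |

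**2. Is the difference explained anywhere?** No. Neither the protocol nor the SAPs limit 6.1.3 to safety reporting or say that it does not apply to tables. Section 12.1 of the Extension SAP, on changes from the protocol, lists efficacy variables only. The same section of the Induction SAP shows no entries. The Induction SAP was written against Amendment 4, but the itemised changes for Amendment 5 alter only the two causality definitions in 6.1.3 and do not record the sentence on unreported causality as new.

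**3. Direction.** For any arm, let R be the number of subjects with at least one Reasonable Possibility event, and U the number with no such event but at least one event lacking causality.

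- Planned drug-related count = R
- Count under 6.1.3 = R + U
- Difference = U, which is zero or positive

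The planned count is therefore never above the 6.1.3 count, and the two are equal when U = 0.

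**4. Size.** U is not given and cannot be derived. Protocol 8.2 plans 210 subjects in six equal groups, so 210/6 = 35 per induction arm. With U as an assumption:

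| Assumed U in one arm | Change in that arm's drug-related percentage |
|---|---|
| 0 | 0 points |
| 1 | 1/35 = 2.9 points |
| 2 | 2/35 = 5.7 points |
| 3 | 3/35 = 8.6 points |

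These values restate the arm size. They are not an estimate of what will happen.

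**The case against.** The case for leaving the plan alone has several sound parts.

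- **The two rules may serve different purposes.** Section 6.1.3 describes how the sponsor regards an event. The SAP overview row and by-relationship tables report the investigator's own assessment, and an event that the investigator did not rate does not fit a row defined by that rating. This is a fair reading, and it is a good reason not to relabel such events as Reasonable Possibility in those rows. But the documents never state the distinction, and they offer no other drug-related summary in which the sponsor's rule is applied.
- **Missing safety data are not to be imputed.** Protocol 8.1.7.1 says so. Section 6.1.3, however, is a classification rule in the same protocol, and nothing says that 8.1.7.1 overrides it.
- **Such events may be rare or absent.** Protocol 6.1 requires the investigator to record the relationship for each event. That stands, although 6.1.3, 8.1.7.2.1 and both SAPs all provide for the case.
- **The subjects are not hidden.** They appear as *unknown* in the by-relationship tables, and *unknown* takes precedence over No Reasonable Possibility for the same event. That stands for those tables, but not for the overview row or the drug-related table.

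A reader might infer more than the documents support. They do not show that drug-related counts are in fact understated, because no rate of missing causality is given. They do not report these events as unrelated to the drug. No bias in the comparison with placebo follows either, since the same rule applies to every arm. Finally, the documents do not say that a causality judged not assessable is coded as unknown, so the conflict is clearest for causality that was not reported.

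**Conclusion.** The plan is wrong as written, in that the protocol contradicts itself and both SAPs carry the contradiction forward. The severity is minor. If any causality is missing, the drug-related counts will be equal to or lower than 6.1.3 implies, by the number of subjects who have an event lacking causality and no event rated Reasonable Possibility. If none is missing, there is no difference. The figure of 2.9 points per affected subject assumes 35 subjects in an induction arm and is only an illustration.

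The reach is limited. Summaries of all treatment-emergent, serious and severe events, deaths, discontinuations and events of special interest do not depend on causality, and no efficacy endpoint is touched. It would also go too far to call the two rules irreconcilable, since a short statement of scope and one added summary resolve the matter.

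**What to change.** In Protocol 8.1.7.2.1 and in section 11.2.1 of both SAPs:

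1. Keep the investigator-rated rows and the *unknown* category as they are.
2. Add a drug-related summary (an overview row, and a table by SOC and preferred term) that counts missing or non-assessable causality as associated under 6.1.3, with a footnote giving the number of events assigned this way.
3. State that this summary applies the 6.1.3 classification and is not an imputation barred by 8.1.7.1.
4. State how a causality judged not assessable is coded in the data.

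The Extension SAP says that the induction analysis was performed separately under its own signed-off SAP, so for induction the addition would be a supplementary summary.

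The cost is a few sentences in each document, one extra row or summary and a small amount of programming. Drug-related counts in the added summary may be slightly higher than in the investigator-rated one.
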